#### b. Clinical and immunological findings in babies at one year; comparison with maternal and cord blood immunological responses.

Analysis period:	Approximately April-September2004.				
· ·	(When babies of mothers enrolled in the first 6 months have reached one year				
	and necessary laboratory data are complete).				
Data to be analysed:	Clinical and laboratory (haematological, parasitological and immunological) results.				
Purpose of analysis:	1. To obtain preliminary data on the effect of maternal helminths and of maternal treatment with albendazole and praziquantel on outcomes in the babies at one year, in particular:				
	• babies' growth				
	• incidence of common disease outcomes in the first year (malaria,				
	diarrhoea, ALRI).				
	
 
neonatal and infant mortality*
 
				
	• babies' immune responses to selected antigens.				
	This data will provide better information on the effects of maternal helminth infections on the response to immunisations in the babies, and for				
	comparisons between helminth species, as well as on the effects of maternal				
	treatment for helminths.				
	2. To examine the effect of albendazole and praziquantel treatment on maternal immune responses by comparing findings at enrolment and delivery in treated and untreated groups.				

	3. To make further comparisons between maternal and cord blood immune
	responses.
	These analyses will make an important contribution to evaluating safety and
	ethical issues regarding the risks and benefits of anti-helminthic treatment in
	pregnancy.
	These analyses will also allow the TSC to re-evaluate the target sample size
	for the cohort.
Comment:	Access to unblinded data required. **

# **GENERAL CONSIDERATIONS.**

\* For some analyses (indicated\*) the sample size at the time point proposed is likely to be insufficient to achieve a statistically significant result.

\*\* Unblinding. Where access to unblinded data is required it is proposed that the analysis be conducted by the principal investigator and project statistician(s), who do not have clinical responsibility for participants. Access to the full data set and analysis programmes will be given to the DMEC. Access to the overall results will be given to scientific staff of the project, collaborators and TSC members.

Data from these analyses, especially from the analyses of the main study, may be publishable. This will be reviewed with the TSC.

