Our initial objective was to establish a cohort that would be sufficiently large to allow analysis of the effects of helminths and their treatment of the incidence of tuberculosis. For this there are, at present, insufficient data to make accurate calculations regarding the sample size required. The incidence of *tuberculosis* in children under five in Entebbe is not known. In a well-documented community in South Africa the incidence in children aged 0-5 years was 3588/100.000 p.a.; 3.5 times the incidence in adults. The estimated overall incidence in Uganda is 320/100,000 p.a. so a figure of 500/100,000 p.a. for children under 5 may be reasonable (Appendix 2C)). A study with 1170 children in each arm and median follow up of 3 years would detect a difference in incidence of 250/100,000 to 750/100,000 cases p.a. between two equal groups (e.g. children of mothers treated with albendazole vs children of mothers treated with placebo). This estimate of effect is large but, if helminths are crucial to the reduced effectiveness of BCG in tropical environments, a large effect is expected. On the other hand, the change in design to include an additional intervention means that the required sample size is likely to be even larger. We therefore propose to review the findings when the study has been running for approximately 18 months. Data regarding the impact of interventions in the mothers on incidence of infectious diseases in the first year of life and on immune responses to tuberculosis antigens one year after BCG immunisation will assist in further planning (appendix 9).

Protocol amendment, January 2009. For *TB infection* among five year olds, where the overall prevalence is expected to be about 15%, the study will have over 90% power, with p<0.05, to detect a difference of 10% vs 20% between either of the interventions in pregnancy, or between the intervention arms in childhood.

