#### a. Clinical findings in mothers and baby at delivery.

Approximately October 2003-January 2004. Analysis period: (When enrolment to the study has completed one year). Clinical and laboratory (haematological and parasitological) results. Data to be analysed: Purpose of analysis: To obtain preliminary data on the effect of albendazole and praziguantel on outcome at delivery for mother and baby, in particular: • maternal post-partum haemoglobin maternal and cord blood viral load in HIV-positive mothers •

- maternal parasite burden •
- eclampsia/ pre-eclampsia\*
- maternal deaths\*
- babies' birth weight
- congenital abnormalities\*
- stillbirths and early neonatal deaths\* •

Access to unblinded data required. \*\*

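### Appendix 9 releases by-arm interim results on the maternal treatments to project staff, collaborators and the TSC, and lets them inform the sample size while enrolment is still open

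*Protocol*

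**What the plan says.** Appendix 9 lists two main-study analyses that need unblinded data. Analysis (a) covers maternal and birth outcomes and is triggered thus: "When enrolment to the study has completed one year". It is dated October 2003 to January 2004. Analysis (b) covers infant outcomes at one year, for babies of mothers enrolled in the first six months, and is dated April to September 2004. Both estimate effects of albendazole and praziquantel given in pregnancy.

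The General Considerations of Appendix 9 set the handling:
- Who runs them: "the analysis be conducted by the principal investigator and project statistician(s), who do not have clinical responsibility for participants".
- The DMEC's part: "Access to the full data set and analysis programmes will be given to the DMEC".
- Who sees the results: "Access to the overall results will be given to scientific staff of the project, collaborators and TSC members".
- Publication: "Data from these analyses, especially from the analyses of the main study, may be publishable", a matter to be taken up with the TSC.

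On sample size, the text for analysis (b) adds: "These analyses will also allow the TSC to re-evaluate the target sample size". The section Sample size estimates says: "We therefore propose to review the findings when the study has been running for approximately 18 months". It names what the maternal interventions do to first-year disease incidence, and to responses to tuberculosis antigens after BCG, as inputs to that planning.

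**The concern.** Malaria, diarrhoea, pneumonia and vaccine responses are principal outcomes, and analysis (b) compares the maternal arms on all of them. Those who run the study and decide its size would know the direction of the treatment differences while mothers are still being enrolled and children are still being followed. The DMEC receives the data but does not control who else sees the results.

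Several choices that shape the final comparison are left open:
- The malaria parasite cut-off is to be set from data on asymptomatic children (Appendix 11).
- The number of ELIspot subjects and the choice of assays depend on preliminary results (Principal Outcomes, Outcome (1)).
- Diarrhoea may follow the mother's own definition (Outcome (3)).
- The cohort size itself is under review.

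Choices made with knowledge of the leading arm are hard to defend afterwards, even if made in good faith. Publishing an arm comparison during enrolment would add to the difficulty.

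**Working it through.** **1. Are these real arm comparisons?** Appendix 7 sizes some outcomes for interim testing. For 10% vs 20%, two-sided 5%, 80% power:
- n = [1.96√(2×0.15×0.85) + 0.8416√(0.1×0.9 + 0.2×0.8)]² / 0.10² = 199 per group.
- With continuity correction: (199/4)×[1 + √(1 + 4/(199×0.10))]² ≈ 219, the protocol's figure.

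The same method returns its 474 per group for 5% vs 10%. Both are labelled feasible at the interim. They concern low birthweight and postpartum anaemia, which are not principal outcomes, but they show that powered by-arm comparisons are intended.

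**2. When do the analyses fall?** Analysis (a) is due after one year of enrolment and is dated from October 2003, which implies a start near October 2002. That puts (a) at about months 12–15 and (b) at about months 18–24. The start date is inferred; the time-line table in Appendix 6 is not readable enough to confirm it.

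**3. How far has enrolment gone?** Establishing the cohort gives 1,200–1,500 deliveries a year, about 70% resident in the study area, and over 90% of those attending the antenatal clinics.
- 1,200 × 0.70 = 840 and 1,500 × 0.70 = 1,050 women a year if every one joins.
- Applying 90% attendance as well: 756 to 945 a year.
- Check against Appendix 2A: 106 deliveries in 4 weeks × 13 × 65/99 ≈ 905 a year, inside these ranges.

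| Month | 840–1,050 a year (% of 2,500) | 756–945 a year (% of 2,500) |
|---|---|---|
| 12 | 840–1,050 (34–42%) | 756–945 (30–38%) |
| 18 | 1,260–1,575 (50–63%) | 1,134–1,418 (45–57%) |
| 24 | 1,680–2,100 (67–84%) | 1,512–1,890 (60–76%) |

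Reaching 2,500 takes 2,500/1,050 = 2.4 to 2,500/840 = 3.0 years, or 2.6 to 3.3 years with the attendance factor. Finishing by month 24 would need 1,250 a year. So both analyses fall within enrolment, and children are followed to age five and, by amendment, to ten.

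**4. What would analysis (b) rest on?** Six months of enrolment is 420–525 mothers, 17–21% of 2,500. One year each, ignoring losses and twins, gives about 420–525 child-years. At the protocol's assumed tuberculosis rate of 500 per 100,000 a year that is 2.1–2.6 cases in all arms together; at 10 pneumonia episodes per 100 person-years it is 42–53. Splitting such counts by arm gives little usable information for sizing.

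**5. Do the provisions fit together?** Appendix 8 leaves the Entebbe copies of the randomisation codes with an uninvolved statistician. Appendix 10 refers to a statistician in charge of the DMEC. The protocol thus has an independent person available, yet Appendix 9 assigns the unblinded work to the project team.

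**The case against.** The protocol is not without safeguards. The analysts have no clinical responsibility. What is released is group-level, so individual allocation stays behind numbered sealed envelopes. Publication goes through the TSC. The analyses are called preliminary and serve a legitimate safety purpose. The review of N is driven largely by unknown tuberculosis incidence and the added praziquantel factor, and no rule ties N to an observed effect. All of this stands, and it narrows the point.

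Several stronger readings are tempting but not supported:
- **That the false-positive rate is inflated.** A reader might infer unadjusted testing at the interim and again at the end. The 5% level in Sample size estimates is a planning input, and a rule for repeated looks may be in the SAP, which is not at hand.
- **That the child trial is unblinded.** Both analyses compare maternal treatment only; the three-monthly albendazole comparison is in neither.
- **That those recording symptoms know a child's arm.** Field workers are not named as recipients, scientific staff is not defined, and group results do not reveal an individual's allocation.
- **That analysis (a) tests principal outcomes.** The protocol says birth outcomes are not its main issue, and only (b) is tied to sample size.
- **That released interim results drove the later amendments.** The 2008 and 2009 amendments mention findings from within the study, but nothing shows that they came from (a) or (b).

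The safeguards protect bedside care and individual masking. They do not keep arm differences from the people who decide sample size, cut-offs, assays and conduct.

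**Conclusion.** The point holds in this limited form and should be fixed. The protocol itself provides for release of by-arm results on the maternal treatments beyond the DMEC, and lets treatment effects inform the review of the target sample size, with about 50–63% of mothers enrolled at month 18 and 67–84% at month 24 (45–57% and 60–76% if 90% antenatal attendance is applied).

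These shares rest on an inferred October 2002 start and on every eligible woman joining. Lower uptake would leave more of enrolment exposed. Women who attend the clinic but deliver elsewhere, or recruitment at the Private Wing, would leave less, and the protocol gives no figures for either. No stated sample size is shown to be wrong, and the size of any resulting bias cannot be computed from the document.

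**What to change.** Reword Appendix 9 as follows:
- The DMEC statistician runs every by-arm interim analysis, and only the DMEC sees the results.
- The principal investigator, project staff, collaborators and TSC receive pooled data and a DMEC recommendation. This serves the safety purpose in full.
- The sample-size review uses pooled event rates such as tuberculosis and pneumonia, not observed arm differences. The pooled tuberculosis count will be small at that stage and should be shown with its uncertainty.
- No arm comparison is published until enrolment, and masked collection of the outcome concerned, are complete.

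The scheduled dates precede the latest amendments. If the analyses have been done, record who saw which results and when, and apply the restriction to the comparisons that remain.

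The cost is a rewritten section, extra runs for the DMEC statistician, and later release and publication of arm-level interim findings.

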#### TIMETABLE.

August 02	ecember 02- ebruary 03	March 03- April 03	October 03- January 04	February 04- April 04	April 04- September 04
pilot (a)	pilot (b)	pilot (c)	main (a)	pilot (d)	main (b)

#### **APPENDIX 10. Serious Adverse Events.**

A serious adverse event will be defined as any clinical event considered by the clinician to be severe or life-threatening, or that results in death. This includes events that require unexpected hospitalisation or prolongation of existing hospitalisation or results in persistent or significant disability or incapacity.

For the purposes of this study, severe adverse events include, but are not limited to: miscarriage, intrauterine death, stillbirth, neonatal death, major congenital abnormality; maternal death or death of the infant/ child; anaphylaxis, severe acute bronchospasm, seizures occurring within 24 hours of administration of the study drug.

Maternal deaths will only be reported as "serious adverse events" if they occur during pregnancy and the puerperium (within 42 days of the end of pregnancy) since no further study intervention will be given to the mothers after the treatment of helminth infections found at delivery. However, death of the mother will be documented if it occurs at any time during follow up of the child.

The likelihood of a causal association between administration of the study drug and a serious adverse event will be defined using definitions adapted from WHO terminology, as follows:

- 1. **Probable:** A clinical event, including laboratory test abnormality, with a reasonable time sequence to administration of the drug, unlikely to be attributed to concurrent disease or other drugs or chemicals.
- 2. **Possible:** A clinical event, including laboratory test abnormality, with a reasonable time sequence to administration of the drug, but which could also be explained by concurrent disease or other drugs or chemicals.
- **3.** Unlikely: A clinical event, including laboratory test abnormality, with a temporal relationship to drug administration that suggests that a causal relationship to administration is unlikely. Other drugs, chemicals or underlying disease provide a plausible explanation.
- 4. Not assessable: A clinical event for which the information received is insufficient to allow reasonable assessment.

A report will be made on any serious adverse event as soon as possible after it occurs, and a copy will be forwarded as soon as possible thereafter to the statistician in charge of the Data Monitoring and Ethical Committee. At his discretion he will consult the DMEC and will inform the chairman of the Trial Steering Committee if there is evidence to suggest that the Steering Committee should consider stopping the study or requesting that an interim analysis should be conducted.

A summary of all reported serious adverse events will be presented at each Trial Steering Committee meeting.

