#### **Specific Aim:**

To examine the impact of helminths on the response to immunisation, and on susceptibility to infectious diseases in childhood, in a cohort of 2500 mothers and their children in Entebbe, Uganda. The study will have three randomised, placebo-controlled comparisons as well as observational components.

1. To examine the effects of maternal infection with intestinal nematodes, and of the treatment of maternal nematode infection in pregnancy. Mothers will be randomised to receive treatment with albendazole or placebo during the second to third trimester of pregnancy.

Mothers who are severely anaemic (haemoglobin  $\leq 8g/dl$ ) will be excluded from randomisation and treated with albendazole.

2. To examine the effects of maternal schistosomiasis, and of the treatment of schistosomiasis in pregnancy. Mothers will be independently randomised to receive treatment with praziquantel or placebo during the second to third trimester of pregnancy.

Mothers who have persistent diarrhoea with blood in the stools will be excluded from randomisation, investigated, and treated for schistosomiasis if present.

Thus the study will comprise four groups of mothers, according to treatment during pregnancy: (1) treated with both albendazole and praziquantel; (2) treated with only albendazole; (3) treated with only praziquantel; (4) no anti-helminthic treatment.

All mothers will have a second stool sample taken at delivery. All mothers will be mass treated with albendazole and praziquantel after delivery.

- **3.** To examine the effects of acquisition of intestinal nematodes during childhood and of regular mass treatment in childhood. After one year of age, children will be randomised to receive albendazole or placebo every 3 months. All children will receive annual, selective treatment based on stool analysis.
- **4.** To examine the effects of childhood schistosomiasis. This component will be observational. Children will receive annual, selective treatment based on stool analysis.

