#### Mothers: treatment of helminths post delivery.

All mothers will receive mass treatment with albendazole 400 mg and praziquantel 40 mg/kg; both drugs will be given as a single stat dose. Mothers found to have *Strongyloides* will be treated with albendazole 400 mg daily for three days. This treatment will be provided when the mother attends the follow up clinic with her baby six weeks after delivery, by which time both her stool results will be available.

Protocol amendment, March 2003. "Effect of praziquantel treatment during pregnancy on antischistosome immune responses in pregnant women and their infants." Mothers who have schistosomiasis will be asked to provide an additional blood sample (maximum volume 30 ml) before this post-delivery treatment, and a further follow-up stool and blood sample (maximum volume 30 ml) a further six weeks later. These samples will allow a comparison of both the immunological and the therapeutic effects of treating schistosomiasis in pregnancy, with the effects of treatment after delivery.

Children: at delivery.

For children, cord blood will be obtained at delivery.

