# These studies will allow a detailed assessment of the impact of helminths on the response to immunisation and on infectious disease incidence. The results will have important practical applications for health policy in the tropics.

#### **Ethical Considerations**

The main ethical consideration for this study is the randomisation of treatment of helminths in pregnancy vs after delivery in mothers, and of mass treatment vs annual, selective treatment in children. Advantages and disadvantages of each intervention are outlined in the proposal. To our knowledge, the only proven benefit of helminth treatment in pregnancy is prevention of hookworm-associated anaemia, so mothers with severe anaemia and hookworm will be excluded from randomisation and treated. Otherwise, risks and benefits of the interventions are not certain and so a randomised design is proposed.

New considerations relating to the proposed change in design, ie to the randomisation of treatment with praziquantel vs placebo during pregnancy followed by selective treatment after delivery are as follows:

- WHO's "Informal Consultation on the use of praziquantel during pregnancy/ lactation, and albendazole/ mebendazole in children under 24 months" recommend that pregnant and breast feeding women should no longer be excluded from treatment with praziquantel, but should be treated in mass treatment programmes or in cases where schistosomiasis is specifically diagnosed. In their report they note that studies of reproductive toxicity in animals showed no harmful effects and that use in breeding animals and in lactating cows is allowed. They also report that several pregnant women have been treated with high doses of praziquantel for cysticercosis without adverse effect and that no reports of adverse outcomes have been made despite the probable, inadvertent treatment of large numbers of pregnant women in mass treatment campaigns.

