#### APPENDIX 3: The impact of helminths on the response to immunisation and on susceptibility to infectious diseases in childhood in Uganda. Proposed Study Profile.

First visit to the antenatal clinic.

• Women who live in study area; no history of adverse effects of anti-helminthics.

Т

- Consent to study of treatment in pregnancy.
- Screening investigations, including Hb, HIV, RPR, immunological studies.
- Provision of antimalarials and haematinics.
- Request stool sample.

	↓
On receipt of stool sample; gestation > 14	weeks; screening Hb results available.

 
Severe anaemia:
 
Treat with albendazole; exclude
 
Persistent diarrhoea with blood:
 
investigate and treat; exclude
 
	
 
Not severe anaemia:
 
Randomise to albendazole or placebo & praziquantel or placebo
 

At delivery.	

 
Mother:
 
Blood and stool samples
 
Nevirapine if known HIV+
 
	

Child:

Cord blood

Nevirapine if mother known HIV+

Post delivery.	↓
• Mass treatment with albendazole and praziquantel; selective treatment for Strongyloides .	• 1-2 samples post immunisation for studies of time course of immune response in selected participants.
	 ▼
	At one year.
	
 
Blood and stool samples
 
Specific treatment for worms found
 
Consent to study of treatment in childhood.
 
Randomisation to receive albendazole or placebo at 3 month intervals, starting at age 15 months
 

	Annual visits.
	Blood and stool

- Blood and stool
- Specific treatment for worms found

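### SAE reporting of maternal deaths ends 42 days after pregnancy, but the last protocol dose is scheduled at six weeks after delivery, so almost no reportable time follows it

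*Protocol*

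**What the plan says.** Protocol, Appendix 10 counts maternal deaths as SAEs only "if they occur during pregnancy and the puerperium (within 42 days of the end of pregnancy". The reason it gives is "since no further study intervention will be given to the mothers after the treatment of helminth infections found at delivery". It adds that a mother's death at any later point in the child's follow-up will be documented. SAE reports go to the DMEC statistician as soon as possible, and a summary of reported SAEs goes to each Trial Steering Committee meeting.

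The post-delivery treatment is described in four other places:

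- Specific Aim: "All mothers will be mass treated with albendazole and praziquantel after delivery".
- The post-delivery treatment section of Procedures, which sets out the regimen: "All mothers will receive mass treatment with albendazole 400 mg and praziquantel 40 mg/kg; both drugs will be given as a single stat dose". For those with *Strongyloides*, the plan is that they "will be treated with albendazole 400 mg daily for three days". On timing, "This treatment will be provided when the mother attends the follow up clinic with her baby six weeks after delivery".
- Appendix 3 (study profile): "Mass treatment with albendazole and praziquantel; selective treatment for" *Strongyloides*.
- Ethical Considerations, on the added praziquantel comparison: "randomisation of treatment with praziquantel vs placebo during pregnancy followed by selective treatment after delivery".

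Appendix 7 defines maternal death as an outcome with the same 42-day limit.

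**The concern.** Appendix 10 justifies its cut-off by drug exposure: once the post-delivery treatment has been given, the mother receives nothing more from the study. That supports a cut-off only if the window stays open for some time after the treatment. On the protocol's own schedule, the window closes on the day of the treatment.

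What is at stake is safety oversight of that dose. Appendix 10 grades causality partly by the time sequence between drug and event, yet for deaths it leaves almost no time after this administration in which an event would be reported. The dose is also not incidental to the study. Ethical Considerations frames the maternal design as treatment in pregnancy versus after delivery. The March 2003 amendment takes samples from mothers with schistosomiasis before this dose and six weeks after it, to compare the two timings. For mothers randomised to placebo, it is their first exposure to that drug within the trial.

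**Working it through.** The protocol states no sample size or event figure on this point, so the check sets two dates and several descriptions side by side.

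**Inputs**
- Reporting window for maternal deaths: to day 42 after the end of pregnancy (Appendix 10).
- Post-delivery dose: six weeks after delivery (Procedures, Mothers: treatment of helminths post delivery).
- *Strongyloides* course: three consecutive days (same section).
- Cohort: 2500 mothers, randomised in a two-by-two layout (Specific Aim).

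**Timing**
- Count delivery as day 0. The nominal dosing day is 6 × 7 = day 42, the last day of the window.
- For a visit on day v, the reportable days after the dosing day are max(0, 42 − v).
- v = 40 gives 42 − 40 = 2 days. v = 42 gives 0 days.
- If the visit is d days late (v = 42 + d), the dose falls d days after the window has closed.
- A three-day course started on day 42 covers days 42, 43 and 44, so it ends 44 − 42 = 2 days outside the window.

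**Number of mothers concerned (upper bounds)**
- All mothers dosed after delivery: up to 2500.
- First exposure to a given drug within the trial: 2500 / 2 = 1250 per placebo comparison.
- First exposure to both drugs within the trial: 2500 / 4 = 625.

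These counts assume equal allocation and that every mother attends. They are numbers of women dosed, not numbers of missed deaths. Appendix 7 puts maternal mortality below 1%, but the protocol gives no rate for deaths after day 42, so no expected number can be derived.

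**What is given after delivery**

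| Section | Who is treated |
|---|---|
| Specific Aim | all mothers |
| Procedures, post delivery | all mothers, at six weeks |
| Appendix 3 | all mothers; selective for *Strongyloides* only |
| Ethical Considerations | selective |
| Appendix 10 | infections found at delivery |

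The first three agree with each other. The last two describe a treatment that depends on diagnosis. Appendix 10 does not say when its treatment is given. If it means treatment close to delivery, it conflicts with the six-week schedule. If it means the six-week treatment, the window closes on the day of that treatment. On either reading, the stated reason does not support stopping at day 42.

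**The case against.** The strongest reply is that Appendix 10 does not deny a post-delivery treatment. It makes an exception for it, and no maternal study drug is scheduled afterwards. The phrase about infections found at delivery also has a source in the plan, since the delivery stool sample guides *Strongyloides* treatment. This stands: it would be wrong to read Appendix 10 as saying that no study drug follows delivery. The excepted treatment is nevertheless the one scheduled for day 42.

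A second reply is that 42 days is the protocol's own definition of maternal death. That is a good reason to keep it as the outcome definition in Appendix 7. It does not settle how long drug-related reporting should last, which Appendix 10 argues from exposure.

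A reader might infer several stronger conclusions that the protocol does not support:

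- *That the comparison of treatment in pregnancy with treatment after delivery has no reportable deaths on the after-delivery side.* Deaths among placebo mothers from pregnancy to day 42 are reportable exactly as in the active arms.
- *That a randomised comparison is biased.* All four groups receive the post-delivery treatment under the same window, so the cut-off introduces no difference in ascertainment between arms.
- *That the data are lost.* Later deaths are documented, and Appendix 9 gives the DMEC the full data set for its planned unblinded analyses. What is missing is the prompt route and the SAE summary.
- *That serious reactions to the dose go unreported.* The 42-day limit applies to maternal deaths only. Severe or life-threatening events, unexpected hospitalisation, anaphylaxis, bronchospasm and seizures carry no such limit.

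**Conclusion.** The point holds as a gap in safety reporting. Reportable time for maternal deaths after the last scheduled protocol dose is a few days at most for early attenders, zero for a mother seen on day 42, and none for a mother seen late. Up to about 2500 mothers are affected. The number of deaths that would go unforwarded cannot be estimated from the protocol and is probably small.

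The conclusion rests on two readings: that six weeks means about day 42, and that the mass treatment in the Procedures section is the current plan. If the selective description were the current one, fewer mothers would be dosed, but the timing problem would remain for those treated at six weeks. No efficacy endpoint or randomised contrast is affected. The correction is modest and worth making, because under the present wording the most serious maternal event is the only one subject to the cut-off.

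**What to change.** 1. In Appendix 10, make maternal deaths reportable as SAEs until the later of 42 days after the end of pregnancy or a pre-stated interval after the mother's post-delivery study dose (after the last dose, where a course is given). The interval is for the sponsor and the DMEC to choose and state.
2. Rewrite the reason so that it refers to the post-delivery treatment as actually scheduled.
3. Leave the outcome definition of maternal death in Appendix 7 unchanged.
4. Reconcile Ethical Considerations and Appendix 10 with the Specific Aim, the Procedures section and Appendix 3 on what is given after delivery, to whom and when. This review does not say which description is right.

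The cost is one paragraph in Appendix 10 and a wording correction wherever the descriptions differ. Mothers' deaths are already documented throughout the child's follow-up, so no new data collection is needed. The only operational change is that deaths in the added interval are forwarded to the DMEC statistician and included in the SAE summary for the Trial Steering Committee.
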